5 CRITERIA FOR EVALUATION

5.1 Primary Efficacy Endpoint

The primary endpoint is binary, with each patient classified as either a platelet responder or a platelet non-responder. Platelet responders are defined as patients with ≥ 3 of 4 platelet measurements $>50 \times 10^9/L$ between Weeks 6-12. All platelet counts will be reported, and the four measurements closest in time to Weeks 6, 8, 10, and 12 will be selected for the determination of the primary endpoint. Within a sliding one-week window, only one measurement can be selected.

Patients will be classified as non-responders for any of the following reasons:

- 1) Failing to meet the criteria to be a responder (including having an insufficient number of values $>50 \times 10^9/L$ due to missing data); or,
- 2) Requiring rescue medication at any time within the first 12 weeks of therapy; or,
- 3) Withdrawing from protocol therapy prior to week 6.

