9 STUDY PROCEDURES AND GUIDELINES

EVALUATIONS ¹ WEEK 0-12	SCREENING/DAY 0									UNSCHEDULED VISITS ¹⁰
		72H	W1	W2	W3	W4	W6	W8	W10	
ELIGIBILITY CHECKLIST	x									
PHYSICAL EXAM	x	x ²		x ²				x ²	x	
BLEEDING ASSESSMENT	x	x	x ³	x ³	x			x	x	
TELEPHONE VISIT			x	x						
DEMOGRAPHIC FORM	x									
BASELINE FORM	x									
CONCOMITANT MEDICATIONS	x	x		x			x	x		
OPHTHALMIC ASSESSMENT	x				As needed					
30 DAY FOLLOW-UP ⁴				As needed						
AE/SAE FORM				As needed						
RESCUE MED FORM				As needed						
HRQOL: KIT	x	x		x			x			
HOCKENBERRY FATIGUE SCORE	x	x		x			x			
PROMIS	x						x			
GLOBAL RATE OF CHANGE		x		x			x			
PLATELET COUNT ^{5, 6}	x	x	x	x	x	x	x	x	x ⁶	
CBC ⁵	x				x			x	x	
AST, ALT, TBILI ⁵	x ⁷		x ⁸		x ⁸	x ⁸	x ⁸	x ⁸	x	
DIR COOMBS	x ⁷									
LDH, RETIC ⁵	x ⁷						x			
CREATININE	x ⁷									
PREGNANCY TEST ⁵	x ⁷			x ⁸			x			
FE, TIBC, %SAT FERRITIN ⁵	x ⁷						x			

TREGS ⁹	x	x
SAMPLES FOR BANKING (OPTIONAL)	x	x

¹ 72H time point may occur +/- 24h. Week 1 – Week 4 procedures may occur +/- 72h.

Week 6 – Week 12 procedures may occur +/- 1 week, as long as procedures are separated by at least 1 week:

² Visits may be performed via telehealth when clinically appropriate if necessary for pandemic-related safety or research restrictions

³ Telephone administration of modified Buchanan scale

⁴ Patients will be followed for safety 30 days after the last dose of study treatment

⁵ Local labs (performed at outside lab not associated with ICON site) are acceptable for labs obtained between study visits

⁶ All platelet counts during Week 5 – Week 12 should be reported. Additional platelet measurements between the scheduled Week 6, 8, 10, and 12 measurements should be reported as unscheduled visits.

⁷ May use previously obtained values for screening assessments if done within past 7 days

⁸ Patients on eltrombopag arm only (for duration of eltrombopag administration)

⁹ Performed at central study lab

¹⁰Physical Exam, Bleeding Assessment, Concomitant Medications, Platelet count, and/or CBC to be performed at unscheduled visits when applicable

EVALUATIONS ¹ 4 MOS – 1 YR	4 MOS ²	5 MOS ²	6 MOS	7 MOS ²	8 MOS ²	9 MOS ²	10 MOS ²	11 MOS ²	1 YEAR	UNSCHEDULED VISITS ⁹
PHYSICAL EXAM			x ³				x ³	x		
BLEEDING ASSESSMENT							x	x		
CONCOMITANT MEDICATIONS			x				x	x		
OPHTHALMIC ASSESSMENT					As needed					
AE/SAE FORM					As needed					
RESCUE MED FORM					As needed					
30-DAY FOLLOW-UP ⁴					As needed					

END OF STUDY FORM	x ⁵									
HRQOL: KIT	x									

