14 DATA SAFETY MONITORING

The Boston Children's Hospital will establish a Data Safety Monitoring Committee (DSMC) to review data relating to safety and efficacy, to conduct and review interim analyses, and to ensure the continued scientific validity and merit of the study, according to a DSMC Charter to be established for this protocol. There will be 2 interim review(s) conducted by the DSMC for the purpose of monitoring study conduct and assessing patient safety. Further details regarding the timing and content of the interim reviews is included in the statistical section below.

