To address the primary objective, we will first test for normality of the distribution of the proportion of platelet responders. If the assumption of normality is upheld, a one-sided Cochran-Mantel-Haenszel (CMH) test, at alpha=0.025, will be used to compare the proportion of platelet responders between the two arms. If the normality assumption is violated, then a one-sided Fisher's exact test will be used. The monitoring boundaries and levels of significance for the interim and final analyses of the primary endpoint are detailed in Table 16A. If a monitoring boundary is crossed in an interim analysis, an independent Data Safety Monitoring Board (DSMB) will make a non-binding recommendation regarding trial conduct or potential closure. In the final analysis, we will reject the null hypothesis if the upper (efficacy) boundary z-value of 1.99302 is crossed; in that case, it will be reasonable to conclude that the rate of platelet response is significantly greater in patients treated with eltrombopag than standard first-line treatments. Otherwise, we will conclude that there is insufficient evidence to support superiority of eltrombopag over standard first-line treatments. All randomized patients will be analyzed in the ITT analysis.

Selection of platelet measurements for the determination of platelet response.

All platelet counts will be reported, and the four measurements closest in time to Weeks 6, 8, 10, and 12 will be selected for the determination of the primary endpoint. Within a sliding one-week window, only one measurement can be selected. Patients who have <3 platelet measurements due to missing data will be classified as non-responders.

c. Analysis of Secondary Endpoints

Analyses of all secondary endpoints will be performed in the subset of evaluable patients. To determine the effects of missing data, sensitivity analyses will be performed using two approaches: a) assuming missing at random; and, b) assuming missing not at random. For each secondary endpoint, the assumption of normality will be tested. If violated for binary endpoints, a Fisher's exact test will be used. If violated for continuous endpoints, a Wilcoxon rank-sum test will be used.

To address secondary objective 3.2.1, the Cochran-Mantel-Haenszel test will be used to compare the proportion of patients with poor WHO Bleeding Score and poor Modified Buchanan Score between the two arms.

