To monitor for early evidence of efficacy or lack of efficacy (futility), we will perform group sequential analyses for a total of three “looks” at the data. Power calculations were performed using PASS 14 (NCSS, LLC. Kaysville, Utah, USA). We will conduct two interim analyses using a two-sided Cochran-Mantel-Haenszel test to compare the proportion of platelet responders between the two treatment arms, after 33% and after 67% of randomized patients are accrued. If the trial has not been terminated due to efficacy or futility, the third and final analysis will be conducted after accrual of all randomized patients at the end of the trial. We used the O’Brien-Fleming spending function to determine the monitoring boundaries for these three group sequential tests (Table 16A, Figure 1). For interim analysis 1, significant evidence that the experimental drug is more efficacious than the standard of care will have been provided if we observe a z-test statistic ≥ 3.71 . Significant evidence that the experimental drug is less efficacious than the standard therapy will have been provided if $z \leq -3.71$. For

interim analysis 2, significant evidence that the experimental drug is efficacious or not will have been provided if $z \geq 2.51$ or ≤ -2.51 , respectively. For the final analysis, significant evidence of the efficacy of the experimental drug will have been provided if $z \geq 1.99302$. The members of the study committee will remain masked to the results of the interim analyses. Because the results of this trial will set a new standard of care for this patient population, an independent Data Safety Monitoring Board (DSMB) will make a non-binding recommendation if/when it is appropriate to close the trial early on the basis of the statistical evidence.

[figure not shown]
Table 16A: Interim analysis monitoring boundaries and operating characteristics

Look	Proportion accrued	Lower Bndry	Upper Bndry	Nominal Alpha	Alpha Spent	Total Alpha	Power Spent	Total Power
1	0.33	-3.7103	3.7103	0.0002	0.0002	0.0002	0.02009	0.0201
2	0.67	-2.51142	2.51142	0.012	0.0119	0.0121	0.41425	0.4343
3	1	-1.99302	1.99302	0.0463	0.0379	0.05	0.38006	0.8144

Definitions:

- Nominal alpha: the significance level to be used for a single, standalone test at each interim test.
- Alpha spent: the amount of alpha spent by this interim test.
- Total alpha: the total amount of alpha that is used up to and including the current test.

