In summary, a total of up to 162 (estimated: 147 informative + 15 non-informative) patients will be enrolled and randomized 2:1 to the experimental treatment arm (N=108) and standard treatment arm (N=54). All randomized patients will be included in the ITT analysis of the primary objective.

We anticipate enrolling 45 patients per year (3.7 patients per month). The total accrual duration is expected to be about 3 years, plus 1 year follow-up on the last patient, for a total study duration of 4 years.

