17 DATA COLLECTION, RETENTION, AND MONITORING

a. Data Collection Instruments

The Investigator will prepare and maintain adequate and accurate source documents designed to record all observations and other pertinent data for each subject treated with the study drug.

Study personnel at each site will enter data from source documents corresponding to a subject's visit into the protocol-specific electronic Case Report Form (eCRF) when the information corresponding to that visit is available.

Subjects will not be identified by name in the study database or on any study documents to be collected by the Sponsor (or designee), but will be identified by a site number, subject number and initials.

For eCRFs: If a correction is required for an eCRF, the time and date stamps track the person entering or updating eCRF data and creates an electronic audit trail.

The Investigator is responsible for all information collected on subjects enrolled in this study. All data collected during the course of this study must be reviewed and verified for completeness and accuracy by the Investigator. A copy of the CRF will remain at the Investigator's site at the completion of the study.

b. Data Management Procedures

The data will be entered into a validated database. The Data Management group will be responsible for data processing, in accordance with procedural

documentation. Database lock will occur once quality assurance procedures have been completed.

All procedures for the handling and analysis of data will be conducted using good computing practices for the handling and analysis of data for clinical trials.

c. Data Quality Control and Reporting

After data have been entered into the study database, a system of computerized data validation checks will be implemented and applied to the database on a regular basis. The study database will be updated in accordance with the resolved queries.

Archival of Data

The database is safeguarded against unauthorized access by established security procedures; appropriate backup copies of the database and related software files will be maintained.

At critical junctures of the protocol (e.g., production of interim reports and final reports), data for analysis is locked and cleaned per established procedures.

d. Availability and Retention of Investigational Records

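### Does timing the interim looks by accrual, with no stated data cut for a 12-week endpoint, damage the group sequential design?

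*Combined protocol and SAP*

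**What the plan says.** Section 16.e plans two interim looks and a final analysis of the platelet-responder proportion, using O'Brien-Fleming-type spending. The interim looks come "after 33% and after 67% of randomized patients are accrued", and Table 16A indexes them by proportion accrued.

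Section 5.1 builds the endpoint from counts near weeks 6, 8, 10 and 12. It also makes a patient a non-responder for "Requiring rescue medication at any time within the first 12 weeks of therapy". Footnote 1 to the first schedule in section 9 adds that the week 6 to 12 "procedures may occur +/- 1 week, as long as procedures are separated by at least 1 week". A response is therefore final only at week 12, or week 13 with the window.

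On handling, section 14 has the DSMC conduct and review the interim analyses under a charter still to be established, and adds: "Further details regarding the timing and content of the interim reviews is included in the statistical section below". Section 17.c says that for interim reports "data for analysis is locked and cleaned per established procedures". Section 16.b says: "Patients who have <3 platelet measurements due to missing data will be classified as non-responders". None of these says how to treat a patient whose week 12 has not yet arrived.

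Section 16.e also reviews adverse events at both looks, but words its temporary halt to accrual for the first look only.

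**The concern.** The printed boundaries assume that one third and two thirds of the information is in hand. Accrual runs ahead of outcomes by 12 to 13 weeks, so a look run on the trigger date would hold less information than Table 16A assumes.

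The text leaves three options: wait for the recent patients, leave them out, or score them as non-responders under the missing-count rule. These give different look-2 statistics. Table 16A places 0.414 of the 0.814 total power at look 2, so this is the main opportunity to stop early. In an open-label trial one would like such a choice fixed in advance. Section 14 refers to the statistical section for timing, and that section does not settle it.

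**Working it through.** **The plan's own figures.** Solving the O'Brien-Fleming-type spending bounds at information 1/3, 2/3 and 1 (two-sided 0.05) gives 3.7103, 2.5114 and 1.9931, matching Table 16A. Sequential power at 98 against 49 patients, 75% against 50%, is 0.807 (pooled variance, continuity correction), near the stated 0.8144. Sample size: 147 / (1 − 0.09) = 161.5, so 162.

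**Patients pending at a trigger.** Section 16.f gives 45 patients per year, and also says "The total accrual duration is expected to be about 3 years", which for 162 patients is 54 per year.
- 45 × 12/52 = 10.4; with the window, 45 × 13/52 = 11.3
- 54 × 12/52 = 12.5; with the window, 54 × 13/52 = 13.5

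Share of look 1 (54 patients): 10.4/54 = 19% to 13.5/54 = 25%. Share of look 2 (108 patients): 10.4/108 = 10% to 13.5/108 = 12.5%. These are upper figures, because patients already rescued, or off protocol therapy before week 6, are already non-responders.

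**Type I error.** With pending patients omitted, information is (54 − 13.5)/162 = 0.25 to (54 − 10)/162 = 0.27 at look 1, and (108 − 13.5)/162 = 0.58 to (108 − 10)/162 = 0.60 at look 2. The printed bounds then spend 0.0509 to 0.0512 two-sided in total, against 0.0500 planned. Simulated one-sided error is 2.4 to 2.5% under all three treatments.

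**Power and early stopping.** Stratified CMH simulation: 162 patients, six strata of 27, blocks of 3, 2:1 allocation, printed bounds. Response rates carry the plan's 9% dilution: 0.75 × 0.91 = 0.6825 and 0.50 × 0.91 = 0.455.

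| Treatment of pending patients | Stop at look 1 | Stop at look 2, 10 pending | Stop at look 2, 13 pending |
|---|---|---|---|
| Wait for outcomes | 1.4% | 39.5% | 39.5% |
| Omit | 0.7–0.8% | 35.9% | 34.8% |
| Score as failures | 0.2–0.3% | 30.7% | 28.1% |

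Overall power is 79.5 to 79.8% in every case.

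**Expected enrolment.** A stop at the trigger saves 108 patients (look 1) or 54 (look 2). A stop after waiting saves 10 or 13 fewer. This assumes immediate analysis and that a crossed boundary is acted on.
- Wait, 10 pending: 162 − 0.014 × 98 − 0.395 × 44 = 143.2
- Omit, 10 pending: 162 − 0.008 × 108 − 0.359 × 54 = 141.8
- Failures, 10 pending: 162 − 0.003 × 108 − 0.307 × 54 = 145.1
- Wait, 13 pending: 162 − 0.014 × 95 − 0.395 × 41 = 144.5
- Omit, 13 pending: 162 − 0.007 × 108 − 0.348 × 54 = 142.5
- Failures, 13 pending: 162 − 0.002 × 108 − 0.281 × 54 = 146.6

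**Omitting and recomputing the bounds.** The spending function would move the look-2 bound to about 2.66 (10 pending) or 2.70 (13 pending). Crossing by look 2 at 2.511 is 36.6% and 35.4%, which implies mean statistics of 2.511 − 0.342 = 2.169 and 2.511 − 0.375 = 2.136. Crossing then becomes 1 − Φ(2.66 − 2.169) = 31% and 1 − Φ(2.70 − 2.136) = 29%. Ignoring look 1, expected enrolment is 162 − 0.31 × 54 = 145.3 and 162 − 0.29 × 54 = 146.3, about 2 above waiting.

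**The case for a change.** The strongest case for a change is that interim rules should leave nothing to whoever runs the analysis, and that one sentence would settle this. Section 16.e does not name the cohort, section 14 sends the reader there, and the charter is not among the documents. Failing to stop at look 2 when stopping was warranted has a cost, and the scored-as-failures reading lowers that chance by 9 to 11 percentage points.

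The silence is real, and so is the drop in early stopping. Three things limit the weight of the argument. First, section 16.e times the final analysis in similar terms, after accrual of all patients, and there it cannot mean the day the last patient is randomised. The comparison is imperfect, because the final look also carries the words about the end of the trial, but it shows that waiting is a permitted reading. Second, a count that is not yet due is not plainly missing, so the worst reading is also the least likely. Third, stopping probability alone overstates the gain from waiting, since waiting enrols the patients that an earlier stop would have spared.

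The halt wording is a separate matter. It is a silence after look 1 and contradicts nothing. Section 11.2 requires rapid reporting of serious events, section 14 gives the DSMC a safety remit, and section 16.e reviews adverse events at look 2 as well. How these sections read together is for the sponsor and the DSMC; it does not bear on efficacy timing.

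**Conclusion.** No change to the plan is needed. The missing data cut is an operational detail that the DSMC charter and the interim data lock would ordinarily settle, and the accrual wording leaves room to do so. If the looks wait, the printed boundaries are exact. If they do not, overall power and type I error are essentially untouched, and look-2 stopping falls by about 4 to 5 points with pending patients omitted under the printed bounds.

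Waiting is a trade-off with no clear gain. Expected enrolment under waiting is about 1 to 2 patients higher than omitting under the printed bounds, and about 2 lower than omitting with recomputed bounds or scoring pending patients as failures. Each efficacy look would also come about 3 months later. If the safety review stayed at the accrual points, there would be four review dates against the two in section 14.

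This rests on uniform accrual at 45 to 54 patients per year, the plan's response rates with 9% dilution, and treating every recent patient as undetermined, which overstates the effect. A crossed boundary yields only a non-binding recommendation, so the practical effect is smaller still.
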